# 14.3. Exploratory Efficacy

The exploratory efficacy analyses and QoL will be performed for the FAS.

Summary statistics will be provided in terms of absolute value and changes from baseline for each visit.

Document: BIOSdata\argenx\Efgartigimod\HAB40220\Biostatistics\Documentation\SAP

Author: Version Number: 3.0

Version Date: 02 May 2024

Template No.: CS\_TP\_BS016 Revision 7 Reference: CS\_WI\_BS005

Effective Date: 01Nov2021

Copyright © 2009, 2010, 2012, 2016, 2018, 2019, 2021 IQVIA. All rights reserved. The contents of this document are confidential and proprietary to IQVSystatingselrsicand ItsOsluStataries Alphanthocided Visas IdisObDureVoVraQiodIDEureVoVraQiodIDEureVoVraQiodIDEureVoVraQiodIDEureVoVraQiodIDEureVoVraQiodIDEureVoVraQiodIDEureVoVraQiodIDEureVoVraQiodIDEureVoVraQiodIDEureVoVraQiodIDEureVoVraQiodIDEureVoVraQiodIDEureVoVraQiodIDEureVoVraQiodIDEureVoVvraQiodIDEureVoVraQiodIDEureVoVraQiodIDEureVoVraQiodIDEureVoVraQiodIDEureVoVraQiodIDEureVoVraQiodIDEureVoVraQiodIDEureVoVraQiodIDEureVoVraQiodIDEureVoVraQiodIDEureVoVraQiodIDEureVoVraQiodIDEureVoVraQiodIDEureVoVraQiodIDEureVoVraQiodIDEureVoVraQiodIDEureVoVVraQiodIDEureVoVraQiodIDEureVoVraQiodIDEUreVoVraQiodIDEUreVoVraQiodIDEUreVoVraQiodIDEUreVoVVVraQiodIDEUreVoVVVV

14.3.3.

Page 42 of 64

14.3.2.

14.3.4.

Document: BIOSdata\argenx\Efgartigimod\HAB40220\Biostatistics\Documentation\SAP

Author: Version Number: 3.0

Version Date: 02 May 2024

[figure not shown]
Template No.: CS\_TP\_BS016 Revision 7 Reference: CS\_WI\_BS005

Effective Date: 01Nov2021

Copyright © 2009, 2010, 2012, 2016, 2018, 2019, 2021 IQVIA. All rights reserved. The contents of this document are confidential and proprietary to IQVIAy staddings in cand Its biddings in the contents of this document are confidential and proprietary to IQVIAy staddings in cand Its biddings in the contents of this document are confidential and proprietary to IQVIAy staddings in cand Its biddings in the contents of this document are confidential and proprietary to IQVIAy staddings in the contents of this document are confidential and proprietary to IQVIAy staddings in the contents of this document are confidential and proprietary to IQVIAy staddings in the contents of this document are confidential and proprietary to IQVIAy staddings in the contents of the contents of this document are confidential and proprietary to IQVIAy staddings in the contents of the contents o

Page 43 of 64

# 15. PHARMACODYNAMIC ANALYSIS

Pharmacodynamic (PD) effect of efgartigimod will be assessed via, Total IgG. PD analyses will be performed

Document: BIOSdata\argenx\Efgartigimod\HAB40220\Biostatistics\Documentation\SAP

Author: Version Number: 3.0

Version Date: 02 May 2024

Template No.: CS\_TP\_BS016 Revision 7 Reference: CS\_WI\_BS005

Effective Date: 01Nov2021

Page 44 of 64

in the SAF for the IAWK12, IAWK24 and FPA.

Total IgG will be summarized using descriptive statistics at each analysis visit. Absolute values, changes from baseline, and percent reduction from baseline will be presented. In addition to the planned time points, the following time points will also be shown:

- Maximum drop from baseline
- Minimum postbaseline value

Additionally, lines chart showing change in Total IgG over time will be prepared.

- Charts of IgG % change from Baseline by time for each Subject will be generated for the IAWK12 and IAWK24.
- The mean values to week 12 will be charted by line plot with SE (error bars) by week and by treatment for the IAWK12.

All PD data will be listed.

## 16. IMMUNOGENICITY ANALYSIS

Incidence and prevalence of antidrug antibodies (ADA) against efgartigimod will be assessed in the SAF for the FPA. ADAs to efgartigimod is measured at the time points specified in the schedule of activities of protocol, primarily at baseline, week 1, 4, 12, 24, and SFV.

Immunogenicity samples are analyzed in a 3-tiered approach:

- All samples are evaluated in the ADA screening assay and are scored ADA screening positive (tier 1) or negative.
- If a sample is scored positive in the ADA screening assay, it is further evaluated in the confirmatory assay (tier 2) and is scored confirmed positive (positive immuno-depletion) or confirmed negative (negative immuno-depletion).
- If a sample is scored as confirmed positive, the samples are further characterized in the ADA titration assay (to determine titer).

If available, a titer result will be reported for the ADA confirmed positive samples. However, a titer result is not always available:

• If the ADA confirmed positive sample could not be run in the titration assay (e.g., due to insufficient sample volume/quality to perform the titer analysis), the result will be described as "positive immuno-depletion", and the sample should be considered ADA positive.

Document: BIOSdata\argenx\Efgartigimod\HAB40220\Biostatistics\Documentation\SAP

Author: Version Number: 3.0

Version Date: 02 May 2024

Template No.: CS\_TP\_BS016 Revision 7 Reference: CS\_WI\_BS005

Page 45 of 64

- If a sample is negative in the titration assay, it will be reported as "negative titer", but it should be considered ADA positive because it was confirmed positive in the second tier.
- If a sample could not be analyzed or reported as "positive screen", the ADA sample status is ADA unevaluable.

An overview of this 3-tiered approach and all possible ADA sample results that will be reported by the laboratory is given below. From these reported ADA sample results, a final ADA sample status must be derived during the statistical analysis, as presented in the final column ("Final ADA Outcome"):

Document: BIOSdata\argenx\Efgartigimod\HAB40220\Biostatistics\Documentation\SAP

Author: Version Number: 3.0

Version Date: 02 May 2024

[figure not shown]
Template No.: CS\_TP\_BS016 Revision 7 Reference: CS\_WI\_BS005

Effective Date: 01Nov2021

Page 46 of 64

Statistical Analysis Plan

Figure 1: ADA Sample Status

<sup>a "Positive titer" is reported if it was not possible to retrieve a numerical value.

#### Participant Classification for ADA Against Efgartigimod

Table E below gives an overview of how the ADA participant classification will be derived, starting from the participant baseline ADA sample status.

Document: BIOSdata\argenx\Efgartigimod\HAB40220\Biostatistics\Documentation\SAP

3.0 Author: Version Number:

> Version Date: 02 May 2024

Template No.: CS\_TP\_BS016 Revision 7 Reference: CS\_WI\_BS005

Effective Date: 01Nov2021

Copyright © 2009, 2010, 2012, 2016, 2018, 2019, 2021 IQVIA. All rights reserved. The contents of this document are confidential and proprietary to IQVSAystatringselms.cand Its0sUstationers.A.Lyoputhorided Vsau kitsd [contact] prohibited.

Page 47 of 64

Table J: Participant Classification for ADA Against Efgartigimod

	Highest a postbaseline sample status			
Participant ADA classification	ADA negative	ADA positive (missing titer b )	ADA positive (negative titer c or numerical titer value)	ADA unevaluable
Baseline ADA sample status				
ADA negative	ADA negative	Treatment- induced ADA	Treatment-induced ADA	ADA unevaluable
ADA positive (missing titer b )	Treatment- unaffected ADA	ADA unevaluable	ADA unevaluable	ADA unevaluable
ADA positive (negative titer c or numerical titer value)	Treatment- unaffected ADA	ADA unevaluable	Titer <4x baseline titer:  Treatment- unaffected ADA  Titer ≥4x baseline titer:  Treatment- boosted ADA ADA	ADA unevaluable
ADA unevaluable	ADA unevaluable	ADA unevaluable	ADA unevaluable	ADA unevaluable

<sup>a Highest sample status, with order (from low to high): ADA unevaluable, ADA negative, ADA positive ("positive immuno-depletion" or "positive titer"), ADA positive with titer <1 ("negative titer"), ADA positive with titer ≥1 (numerical value selecting the sample with highest titer).

The following definitions will be used in the summary tables:

- ADA evaluable participant = participant classified in any of following categories: ADA negative, treatment-unaffected ADA, treatment-induced ADA, or treatment-boosted ADA. The first 2 categories are classified as "ADA negative", and the latter 2 are classified as "ADA positive";
- ADA incidence = percentage of participants with treatment-induced or treatment-boosted ADA (denominator: number of evaluable participants);
- ADA prevalence = percentage of participants with treatment-unaffected ADA, treatment-induced ADA, or treatment-boosted ADA (denominator: number of evaluable participants);
- ADA unevaluable participant = participant classified as ADA unevaluable or with missing baseline ADA sample or without postbaseline ADA samples (in case no ADA data are available at all, the participant cannot be classified).

Note: A 4-fold difference in titer values is considered significant if a 2-fold serial dilution is applied (= 2 times

 $\label{loss} Document: BIOS data \argenx \end{argent} Efgartigimod \argenvalue BioS data \argenvalue \argenvalue$ 

Author: Version Number: 3.0

Version Date: 02 May 2024

Template No.: CS\_TP\_BS016 Revision 7 Reference: CS\_WI\_BS005

Effective Date: 01Nov2021

Copyright © 2009, 2010, 2012, 2016, 2018, 2019, 2021 IQVIA. All rights reserved. The contents of this document are confidential and proprietary to IQV\$\text{Systecting} = \text{Population} \text{Almost the contents} and Its\text{Sidiaries} \text{Almost the contents} \text{Almost the content

<sup>b Samples with missing titer will have a reported ADA result of "positive immuno-depletion" or "positive titer".

<sup>c Results reported as "negative titer", ie, titer value <1 will be set to a value of 1.

Page 48 of 64

the dilution factor).

**Frequency tabulations** (number and percentages) will be provided with ADA negative/positive/unevaluable samples per visit.

Frequency tabulations (number and percentages) will be provided in 1 table for:

- ADA unevaluable Participants
- ADA baseline positive/negative/unevaluable samples
- Participants per ADA participant classification
- Prevalence and incidence of ADA

**Correlation tables** by ADA against efgartigimod participant classification will be provided for the following parameters:

- Mean drug concentration over time
- Mean percent change from baseline in [total IgG]
- COMPASS-31 and MaPS
- TEAEs by MedDRA SOC and PT
- Serious TEAEs by MedDRA SOC and PT
- Injection/infusion-related reactions

•

- ADA against efgartigimod titer values will be summarized using descriptive statistics by ADA
  participant
- classification at each analysis visit.
- All available data for ADA against efgartigimod will be listed, while also showing the ADA sample status and participant classification.

# 17. BIOMARKER ANALYSIS

Frequency tabulations (number and percentages) for categorical variables and summary statistics for continuous variables will be provided in terms of absolute value and changes from baseline for each visit for below except

Document: BIOSdata\argenx\Efgartigimod\HAB40220\Biostatistics\Documentation\SAP

[figure not shown]
Author: Version Number: 3.0

Version Date: 02 May 2024

Template No.: CS\_TP\_BS016 Revision 7 Reference: CS\_WI\_BS005

Effective Date: 01Nov2021

Page 49 of 64

# 18. SAFETY OUTCOMES

In order to assess the long-term safety and tolerability of efgartigimed in participants, below safety endpoints are considered within primary objective.

- Incidence and severity of AEs
- incidence of SAEs,
- changes in laboratory test results,
- vital signs, and
- electrocardiogram (ECG) results

These endpoints will be assessed and reported based on the SAF.

There will be no statistical comparisons between the treatment groups for safety data, unless otherwise specified with the relevant section.

#### 18.1. Adverse Events

AEs and SAEs will be collected as defined in the section 10.3 of the protocol. AEs will be coded using latest version of Medical Dictionary for Regulatory Activities (MedDRA) central coding dictionary. AEs will be graded using the National Cancer Institute (NCI) Common Terminology Criteria for Adverse Events (CTCAE) version 5.0. For each AE, start and stop date/times are collected as well as severity, a seriousness flag, treatment-relatedness, relatedness to procedures, action taken towards the study drug and outcome.

Document: BIOSdata\argenx\Efgartigimod\HAB40220\Biostatistics\Documentation\SAP

Author: Version Number: 3.0

Version Date: 02 May 2024

Template No.: CS\_TP\_BS016 Revision 7 Reference: CS\_WI\_BS005

Effective Date: 01Nov2021

Contribut © 2000, 2010, 2012, 2016, 2010, 2010, 2021 IOV//A All ci

Page 50 of 64

**Treatment-emergent adverse events (TEAEs)** are defined as AEs with onset on or after the first administration of IMP up to and including 60 days after the last IMP administration before the event (refer to schematic).

D1: IMP start	D40: Start IMP interruption		D120: IMP restart	D160: Start IM	IP disc	D240: Study disc
IMP			IMP			
TE: D1-D40	TE:	Non-TE:	TE:D120-	TE:	Non-	
	D40+60	D101-119	D160	D160+60	TE:	
	days			days	>D220	

AEs will be considered treatment-emergent based on their start date/time. If the AE start date/time is incomplete or missing, the AE will be considered treatment-emergent unless the available part of the AE start or stop date/time provide evidence that the event did not occur within 60 days from last IMP administration before the event.

AE onset and duration will be calculated as follows when start and stop dates are fully known: AE onset day (vs. first administration)

- o AE start date ≥ date of first administration: AE start date date of first administration + 1 day
- o AE start date < date of first administration: AE start date date of first administration
- AE duration (days) =
- AE end date AE start date + 1 day
- Study discontinuation date =
- AE start date + 1 day (when the AE start date is fully known but the AE is not resolved at the end of the study). In this case the duration will be presented as ">x days".

An AE for which the study drug was discontinued is defined as an AE with action taken "drug withdrawn".

**Severity** is classed as mild/ moderate/ severe/ life-threatening/ death. If a participant reports a TEAE more than once within that SOC/ PT, the AE with the worst-case severity will be used in the corresponding severity summaries.

Relationship, as indicated by the Investigator, is classed as "not related" or "related". If a participant reports the

Document: BIOSdata\argenx\Efgartigimod\HAB40220\Biostatistics\Documentation\SAP

Author: Version Number: 3.0

Version Date: 02 May 2024

Template No.: CS\_TP\_BS016 Revision 7 Reference: CS\_WI\_BS005

Page 51 of 64

same AE more than once within that SOC/PT, the AE with the worst-case relationship to IMP will be used in the corresponding relationship summaries.

**AEs leading to discontinuation of IMP** will be identified by using the "Action taken with Efgartigimod/Placebo due to adverse event" from the AE page of the eCRF.

**Adverse event of special interest (AESI)** can be serious or nonserious, related, or unrelated to the IMP or study procedures. Infections are considered AESIs and are defined as events with a PT that falls under the MedDRA SOC 'Infections and infestations'.

Infusion related reactions (IRRs) are defined as all AEs with a MedDRA PT that is listed in either:

- MedDRA Hypersensitivity SMQ broad selection
- MedDRA Anaphylactic reaction SMQ broad selection

•

• MedDRA Extravasation events (injections, infusions and implants) SMQ broad selection, excluding implants and occurs within 48 hours of an infusion/injection, or within 2 days if the AE start time is not available. In case of partially missing AE start date, the AE will be considered an IRR, unless the available parts of the AE start date provide evidence it did not occur within 48 hours of an infusion/injection.

Any deaths during the study are recorded on the "Deaths Details" page of the eCRF. A death case is defined as an AE with outcome 'fatal'. Fatal events will be presented in a summary table presenting overall TEAEs and a data listing along with primary cause of death.

Summary tables will only include TEAEs. However, all AEs reported during the study will be listed. Summary tables by SOC and PT will be sorted alphabetically.

An overview table of AEs will be presented by treatment to show number and percentage of participants with at least one event, and the number of events and the event rate per 100 PYFU, for the SAF at the IAWK12, IAWK24 and FPA for the following;

•

- TEAEs (IAWK12, IAWK24 and FPA)
- Serious TEAEs (IAWK12, IAWK24 and FPA)
- Grade ≥3 TEAEs (IAWK12, IAWK24 and FPA)
- Fatal TEAEs

Document: BIOSdata\argenx\Efgartigimod\HAB40220\Biostatistics\Documentation\SAP

Author: Version Number: 3.0

Version Date: 02 May 2024

Template No.: CS\_TP\_BS016 Revision 7 Reference: CS\_WI\_BS005

Page 52 of 64

- Treatment-related TEAEs according to the Principle Investigator (IAWK12, IAWK24 and FPA)
- Procedures-related TEAEs (FPA Only)
- Serious treatment-related TEAEs (IAWK12, IAWK24 and FPA)
- TEAEs leading to IMP discontinuation (IAWK12, IAWK24 and FPA)
- TEAEs leading to IMP interruption
- TEAEs of special interest (IAWK12, IAWK24 and FPA)
- IRRs (IAWK12, IAWK24 and FPA)

The overview table will also include a 95% Agresti-Min CI (in case <30 participants in each group) or a 95% Newcombe CI (in case of >30 participants in each group) CI for the difference in AE rate between efgartigimod and placebo.

The event rate per 100 PYFU is defined as 100 \* the number of events divided by the sum of the follow-up time during which an event is considered treatment-emergent of all participants per treatment arm expressed in years (i.e. divided by 365.25).

All AEs, including pretreatment events will be listed.

#### **18.1.1. All TEAEs**

Summary tables will only include TEAEs and will be presented by System Organ Class (SOC) and Preferred Term (PT) for each treatment group. Table will contain number and percentage of participants with at least one event and the number of events (except for TEAEs by worst toxicity) for TEAE. These outputs will be provided for:

- TEAEs
- Serious TEAEs
- Nonserious TEAEs
- Grade ≥3 TEAEs

TEAEs by worst toxicity (FPA Only)

- Treatment-related TEAEs
- Procedure-related TEAEs
- Serious treatment-related TEAEs
- TEAEs leading to IMP discontinuation

Document: BIOSdata\argenx\Efgartigimod\HAB40220\Biostatistics\Documentation\SAP

Author: Version Number: 3.0

Version Date: 02 May 2024

Template No.: CS\_TP\_BS016 Revision 7 Reference: CS\_WI\_BS005

Page 53 of 64

- TEAEs of special interest by worst outcome
- IRRs
- Serious IRR (IAWK12, IAWK24 and FPA)

•

# 18.2. Laboratory Evaluations

Results from the central laboratory will be included in the reporting of this study for serum chemistry and hematology, coagulation, urinalysis, serology (eg, viral marker testing), and specialty laboratory parameters. A list of laboratory assessments to be included in the outputs is included in Appendix 2 (Table 2) of the protocol. These are mainly as follows.

**Table K:** Laboratory Assessments

Hematology	RBC count, platelet count, hemoglobin, hematocrit, MCV, MCH, %reticulocytes, WBC count with differential: neutrophils, eosinophils, lymphocytes, basophils, monocytes
Serum chemistry	ALT, AST, albumin, blood urea nitrogen, creatinine, glucose, potassium, chloride bicarbonate, sodium, total protein, calcium, bilirubin (total and direct)
Routine urinalysis	Specific gravity, pH, glucose, protein, blood, ketones, bilirubin, urobilinogen, nitrite, leukocyte esterase, microscopic examination (if blood or protein is abnormal)
Pregnancy testing	Urine test (as needed for WOCBP potential, defined in Section 10.4.1 of the protocol)
Specialty laboratory tests:	CRP, ESR, TSH

Normal ranges are available as provided by the central laboratory and results will be presented in standardized units unless specified otherwise. Clinically significant changes occurring during the study are recorded as an

Document: BIOSdata\argenx\Efgartigimod\HAB40220\Biostatistics\Documentation\SAP

Author: Version Number: 3.0

Version Date: 02 May 2024

Template No.: CS\_TP\_BS016 Revision 7 Reference: CS\_WI\_BS005

Page 54 of 64

AE.

Quantitative laboratory measurements reported as "< X", i.e. BLQ, or "> X", i.e. above the upper limit of quantification (ULQ), will be converted to X for the purpose of descriptive summaries, but will be presented as recorded, i.e. as "< X" or "> X" in the listings. For Toxicity grades the <X and >X will be represented within the scores.

Continuous laboratory parameters will be summarized using descriptive statistics of actual values and changes from baseline at each analysis visit. Categorical parameters will only be listed.

The following summaries will be provided for laboratory data:

Continuous laboratory parameters to be summarized using descriptive statistics of actual values and changes from baseline at each analysis visit for SAF at the IAWK12, IAWK24 and FPA.

Laboratory toxicity grades to be presented as cross-tabulations of the toxicity at each postbaseline analysis visit and at the worst-case analysis visit versus the baseline toxicity for SAF at the IAWK12, IAWK24 and FPA. Laboratory abnormalities as cross-tabulations of the abnormality at each postbaseline analysis visit and at the

The number of participants with treatment-emergent abnormalities will also be shown. The denominator for the percentage is the total number of participants per treatment arm and per analysis visit in the SAF.

worst-case analysis visit versus the baseline abnormality for SAF at the IAWK12, IAWK24 and FPA.

Listing of participants with any post-baseline abnormality or toxicity grade ≥1

#### 18.2.1. Laboratory Specific Derivations

All datapoints obtained after informed consent up to 60 days after IMP discontinuation or database cutoff will be considered.

The following abnormality categories will be defined:

- Low: value < lower limit of normal range
- Normal: lower limit of normal range  $\leq$  value  $\leq$  upper limit of normal range
- High: value > upper limit of normal range
  - Notes:
  - Classification will be done in standardized units, using non imputed values and limits.
  - For the worst-case analysis visits, as defined in section 6.4, an additional category low + high is defined in case there are both low and high post-baseline values.

Toxicity grades will be computed according to the National Cancer Institute (NCI) common toxicity criteria for

Document: BIOSdata\argenx\Efgartigimod\HAB40220\Biostatistics\Documentation\SAP

Author: Version Number: 3.0

Version Date: 02 May 2024

Template No.: CS\_TP\_BS016 Revision 7 Reference: CS\_WI\_BS005

Effective Date: 01Nov2021

Page 55 of 64

adverse events (CTCAE) toxicity grading list (version 5.0). The implementation of these toxicity grades for analysis is presented in appendix 2. Only the parameters described in appendix 2 will be computed, according to the declared limits for each grade.

Only lab parameters specified within the protocol will be analyzed and, only those both in the protocol and in appendix 2 will be considered for toxicity, all others that are in the protocol and not in appendix 2 but have High/Low/Normal will be presented in the abnormality table.

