8.4.6. Adverse Events of Special Interest

An AESI is an AE of scientific and medical concern specific to the sponsor's product or program. An AESI can be serious or nonserious, related or unrelated to the IMP or study procedures. These events will be reported according to the same timeframe as that for SAEs specified in Section 8.4.1 and Section 10.3.4.

Efgartigimod treatment leads to reduced IgG levels. As low IgG levels can be associated with increased infection risks, events under the MedDRA SOC *Infections and infestations* are considered AESIs in this study. These events will be reported according to the timeframe specified in Section 8.4.1 and Section 10.3.4, with the following information provided:

- Causal pathogen
- Location of infection
- Relationship to an underlying medical condition, medical history, and concomitant medications
- Reoccurrence of a previous infection
- Any confirmatory procedure, culture, or urgent medical intervention, if applicable

Participants for whom an AESI has been reported may be temporary interrupted from IMP treatment, as specified in Section 7.1.2.

8.4.7. **AEs of Clinical Interest**

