# **APPENDIX 2. TOXICITY GRADES**

The table below shows how the CTCAE, v5.0: 27 Nov 2017 will be implemented in the analysis.

Paramater	Unit	Grade 1	Grade 2	Grade 3	Grade 4
Alanine amino transferase		>1-3 *ULN	>3-5 *ULN	>5-20 *ULN	>20 *ULN
Albumin	g/L	<lln-30< td=""><30-20	<20	-	</lln-30<>	<30-20	<20	-
	g/dL	<lln-3< td=""><3-2	<2	-	</lln-3<>	<3-2	<2	-
Alkaline phosphatase		>1.0-2.5 *ULN	>2.5-5.0 *ULN	>5.0-20.0 *ULN	>20.0 *ULN
Aspartate amino transferase		>1-3 *ULN	>3-5 *ULN	>5-20 *ULN	>20 *ULN
Bilirubin (total)		>1.0-1.5 *ULN	>1.5-3.0 *ULN	>3.0-10.0 *ULN	>10.0 *ULN
Calcium (ionized) low	mmol/L	<lln-1.0< td=""><1.0-0.9	<0.9-0.8	<0.8	</lln-1.0<>	<1.0-0.9	<0.9-0.8	<0.8
	mg/dL	<lln-4.0< td=""><4.0-3.6	<3.6-3.2	<3.2	</lln-4.0<>	<4.0-3.6	<3.6-3.2	<3.2
Calcium (ionized) high	mmol/L	>ULN-1.5	>1.5-1.6	>1.6-1.8	>1.8
	mg/dL	>ULN-6.0	>6.0-6.4	>6.4-7.2	>7.2
Calcium (corrected) low	mmol/L	<lln-2.00< td=""><2.00-1.75	<1.75-1.50	<1.50	</lln-2.00<>	<2.00-1.75	<1.75-1.50	<1.50
	mg/dL	<lln-8< td=""><8-7	<7-6	<6	</lln-8<>	<8-7	<7-6	<6
Calcium (corrected)	mmol/L	>ULN-2.9	>2.9-3.1	>3.1-3.4	>3.4
high	mg/dL	>ULN-11.5	>11.5-12.5	>12.5-13.5	>13.5
Creatinine		>1.0-1.5 *ULN	>1.5-3.0 *ULN	>3.0-6.0 *ULN	>6.0 *ULN
Glucose (fasting) low	mmol/L	<lln-3.0< td=""><3.0-2.2	<2.2-1.7	<1.7	</lln-3.0<>	<3.0-2.2	<2.2-1.7	<1.7
Potassium low	mmol/L	-	<lln-3.0< td=""><3.0-2.5	<2.5	</lln-3.0<>	<3.0-2.5	<2.5
	mEq/L	-	<lln-3.0< td=""><3.0-2.5	<2.5	</lln-3.0<>	<3.0-2.5	<2.5
Potassium high	mmol/L	>ULN-5.5	>5.5-6.0	>6.0-7.0	>7.0
	mEq/L	>ULN-5.5	>5.5-6.0	>6.0-7.0	>7.0
Sodium low	mmol/L	<lln-130< td="">-	<130-120	<120	</lln-130<>	-	<130-120	<120
	mEq/L	<lln-130< td="">-	<130-120	<120	</lln-130<>	-	<130-120	<120

Document: BIOSdata\argenx\Efgartigimod\HAB40220\Biostatistics\Documentation\SAP

Author: Version Number: 3.0

Version Date: 02 May 2024

Template No.: CS\_TP\_BS016 Revision 7 Reference: CS\_WI\_BS005

Page 62 of 64

Paramater	Unit	Grade 1	Grade 2	Grade 3	Grade 4
Sodium high	mmol/L	>ULN-150	>150-155	>155-160	>160
	mEq/L	>ULN-150	>150-155	>155-160	>160

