Lymphocytes (absolute	giga/L	<lln-0.80< td=""><0.80-0.50	<0.50-0.20	<0.20	</lln-0.80<>	<0.80-0.50	<0.50-0.20	<0.20
count) low	counts/mm 	<lln-800< td=""><800-500	<500-200	<200	</lln-800<>	<800-500	<500-200	<200
Lymphocytes (absolute	giga/L	-	>4-20	>20	-
count) high	counts/mm 	-	>4000-20000	>20000	-
Neutrophils (absolute	giga/L	<lln-1.5< td=""><1.5-1.0	<1.0-0.5	<0.5	</lln-1.5<>	<1.5-1.0	<1.0-0.5	<0.5
count) low	counts/mm 	<lln-1500< td=""><1500-1000	<1000-500	<500	</lln-1500<>	<1500-1000	<1000-500	<500
Platelets	giga/L	<lln-75< td=""><75-50	<50-25	<25	</lln-75<>	<75-50	<50-25	<25
White blood cells	giga/L	<lln-3< td=""><3-2	<2-1	<1	</lln-3<>	<3-2	<2-1	<1
	counts/mm 	<lln-3000< td=""><3000-2000	<2000-1000	<1000	</lln-3000<>	<3000-2000	<2000-1000	<1000

CTCAE= Common Terminology Criteria for Adverse Events; LLN=lower limit of normal; ULN=upper limit of normal, values within normal ranges will be presented as Grade 0 for toxicity outputs.

Note: In case ULN/LLN is higher/lower than the upper/lower limit of grade 1 (or even higher grades), ULN/LLN will be ignored and only the fixed values of CTCAE will be considered.

Document: BIOSdata\argenx\Efgartigimod\HAB40220\Biostatistics\Documentation\SAP

Author: Version Number: 3.0

Version Date: 02 May 2024

Template No.: CS\_TP\_BS016 Revision 7 Reference: CS\_WI\_BS005

Page 63 of 64

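### SAP 18.2.1, read as written, leaves the ungraded direction of eight laboratory analytes, notably high WBC, neutrophils and platelets, without shift or treatment-emergent counts

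*SAP*

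**What the plan says.** SAP 18.2 plans two sets of cross-tabulations on the safety set, at both interim analyses and the final analysis. One is by grade: "Laboratory toxicity grades to be presented as cross-tabulations of the toxicity at each postbaseline analysis visit", with the worst-case visit, against baseline. The other does the same for abnormalities, meaning the Low, Normal and High categories. Section 18.2 adds that participants with treatment-emergent abnormalities will be counted. It names no analytes to be left out.

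SAP 18.2.1 defines Low, Normal and High from the normal range, with a combined category for participants who have both low and high post-baseline values. It then allocates analytes to displays. For grading, "only those both in the protocol and in appendix 2 will be considered for toxicity". For the other display, "all others that are in the protocol and not in appendix 2 but have High/Low/Normal will be presented in the abnormality table". Grading is confined to what Appendix 2 declares: "Only the parameters described in appendix 2 will be computed, according to the declared limits for each grade".

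Appendix 2 has separate low and high rows for calcium, potassium, sodium and lymphocytes. The remaining analytes have limits on one side only; for glucose the single row is "Glucose (fasting) low". The footnote defines the ungraded category: "values within normal ranges will be presented as Grade 0 for toxicity outputs".

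SAP 6.4 derives the worst-case toxicity for each parameter and for each direction (hypo or hyper). SAP 6.5 defines a treatment-emergent abnormality generally, and one of its examples is a glucose value that goes from low at baseline to high afterward.

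**The concern.** The allocation in 18.2.1 works by analyte, while the grading in Appendix 2 works by direction. An analyte in Appendix 2 leaves the Low/Normal/High table altogether, even when only one of its two directions is graded. A result beyond the other limit then has no grade, because no row exists for it. It is not Grade 0 as the footnote words it, because it is not within the normal range. And it is not classed as High or Low in a table, because its analyte has been sent elsewhere. The programmer must either show it as Grade 0 or treat it as missing, and the SAP does not say which.

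Changes in laboratory results are part of the primary safety endpoint. Infections are the adverse event of special interest, for the reason in Protocol 8.4.6: "As low IgG levels can be associated with increased infection risks". High WBC and neutrophil counts are results a safety reader would want to see by arm next to the infection tables. With about 42 participants randomized 2:1, so about 28 and 14, a few individual shifts can be hard to see in a mean. A count of participants who moved from normal to high is the more direct display.

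**Working it through.** The plan states no figure to reproduce. The check is a comparison of three lists, followed by a reading of the sections together.

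**Inputs.** Protocol analytes come from Protocol Table 2 and SAP Table K (for chemistry: "ALT, AST, albumin, blood urea nitrogen, creatinine, glucose, potassium, chloride bicarbonate, sodium, total protein, calcium, bilirubin (total and direct"). Graded directions come from SAP Appendix 2. The allocation rule comes from SAP 18.2.1.

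**Step 1: match Appendix 2 to the protocol.** Counting calcium once, Appendix 2 covers 14 analytes. Alkaline phosphatase is not a protocol test, so 18.2.1 excludes it: 14 − 1 = 13. Two of these 13 have qualified names in Appendix 2 that the protocol does not use: calcium (ionized, corrected) and glucose (fasting). Clear matches: 13 − 2 = 11.

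**Step 2: count directions among the 11 clear matches.**

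| Graded in Appendix 2 | Analytes | Number | Ungraded side |
|---|---|---|---|
| Both directions | potassium, sodium, lymphocytes | 3 | none |
| Low only | WBC, neutrophils, platelets, albumin | 4 | high |
| High only | ALT, AST, total bilirubin, creatinine | 4 | low |

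One-directional: 4 + 4 = 8 of 11.

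**Step 3: sensitivity to the naming question.** If fasting glucose is the protocol's glucose, it adds one low-only analyte: 9 of 12. If calcium is matched as well, it adds one analyte graded both ways: 9 of 13. If glucose is not matched, it belongs with the others outside Appendix 2 and its high values are counted in the Low/Normal/High table.

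**Step 4: follow one result through the rules.** Take a neutrophil count that is normal at baseline and above the upper limit of normal at week 12.

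- Toxicity table: neutrophils are in the protocol and in Appendix 2, so they are graded. Only the low side has limits, so the value has no grade.
- Grade 0: reserved by the footnote for values in the normal range, so it does not describe this value.
- Low/Normal/High table: 18.2.1 reserves this for analytes outside Appendix 2, so neutrophils do not appear.
- Treatment-emergent count: 18.2 and 6.5, read alone, would count it. The allocation rule gives it no table to be counted in.

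**Step 5: set the sections side by side.** If the Low/Normal/High table were meant to hold every analyte, the words in 18.2.1 that limit it to the remaining analytes would have no function. If it was meant to hold only those, the unrestricted commitment in 18.2 is not met for eight analytes (nine with glucose). Either way the sections need reconciling.

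**The case against.** The strongest reply is that the exclusion is inferred. The word that restricts in 18.2.1 is attached to the toxicity grading. Nothing says outright that graded analytes are barred from the abnormality table, while 18.2, 6.4 and 6.5 all speak of laboratory abnormalities generally. Table contents are also deferred to output templates that are not part of these documents. This stands as a reason to call the matter a conflict between sections, not a settled omission. It does not remove the problem: the allocation sentence is the most specific text on the point, and its natural reading makes the two groups exclusive.

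A reader might go further and infer that these results appear in no table and that a safety reader would see no signal. The documents do not support that. Section 18.2 plans descriptive statistics of values and changes at each visit, and section 7.2 includes quartiles and maxima in them. The listing covers any post-baseline abnormality, graded or not, and is readable at this sample size. Protocol 8.3.4 has clinically significant laboratory changes recorded as adverse events, which are then counted by arm.

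Nor would the infection signal be hidden. The event of special interest is defined by MedDRA system organ class and tabulated directly. CRP and ESR are outside Appendix 2 and so, given normal ranges, belong in the abnormality table, though the schedule takes them only at baseline and week 24. High lymphocytes are graded.

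Glucose should not be put on the same footing as WBC. Its Appendix 2 row is for fasting samples, and the protocol lists plain glucose with no dietary restriction. The example in SAP 6.5 is also weak evidence of intent: the same sentence uses a hemoglobin grade, and Appendix 2 as printed has no hemoglobin row, so the examples may be general text.

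Finally, because 6.4 works by direction, treating a high value as Grade 0 in a low-direction table is a sensible default. The footnote simply does not say so.

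**Conclusion.** The point holds as a drafting conflict with a real but limited effect on the safety display. Followed literally, 18.2.1 and Appendix 2 together give no shift-from-baseline and no treatment-emergent count for the ungraded direction of 8 of the 11 clearly matched analytes, or 9 of 12 if fasting glucose is taken as the protocol's glucose. Of the eight, the high side of WBC, neutrophils and platelets is what deserves attention. High albumin and low ALT, AST, bilirubin and creatinine matter less.

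This rests on two assumptions: that the allocation in 18.2.1 is exclusive, which is its natural reading, and that the output templates do not override it, which cannot be checked here. What is missing is the participant count, not the data. The documents give no rate for such abnormalities, so the number of participants affected cannot be estimated.

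**What to change.** Replace the allocation sentence in SAP 18.2.1 with a statement that the Low/Normal/High cross-tabulations and the treatment-emergent abnormality counts cover all protocol laboratory parameters that have a normal range, including those graded in Appendix 2. Toxicity tables would stay limited to the protocol parameters in Appendix 2. This brings 18.2.1 into line with 18.2, 6.4 and 6.5, and makes the glucose naming question immaterial for the abnormality table.

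In the Appendix 2 footnote, define Grade 0 for each toxicity direction as not beyond the limit in that direction. A high neutrophil count is then Grade 0 in the low-direction toxicity table and High in the abnormality table, and no value is left unclassified.

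The cost is two edits to the SAP and a few more rows in an already planned table. No new data, visits or analyses are needed.
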